In addition, the number of days to resolution of the five aggregated symptoms will be compared based on the serum 25D level at Day 14 (<50 ng/mL vs 50 to 100 ng/mL and 50 to 100 ng/mL vs >100 ng/mL), regardless of the assigned treatment group. The comparison will be done using a Chi-square test. Frequency of relapses will be calculated, if possible, to account for potential worsening of symptoms after resolution (defined immediately above), with relapse being defined as achieving an aggregate FLU-PRO Plus[©] score >5 for a minimum of three consecutive days.

The following secondary endpoints will be tested statistically with methods described below, and the nominal p-value will be reported for evaluation:

- The number of days to resolution of five symptoms (trouble breathing, chest congestion, dry or hacking cough, body aches and pains, and chills and shivering), as measured by the FLU-PRO Plus[©] questionnaire, with resolution defined as the first aggregate symptom score of ≤5 which is maintained for a minimum of three consecutive days (see Section 5.2), with no individual symptom score >1;
- Resolution, defined as the first score of ≤5 which is maintained for a minimum of three consecutive days (without subsequent relapse), for the aggregate five COVID-19 symptoms (trouble breathing, chest congestion, dry or hacking cough, body aches and pains, and chills and shivering) and for each individual symptom, defined as a score of 0 or 1, as measured by the FLU-PRO Plus[©] questionnaire as of Day 10;
- 3. Incidence of emergency room/urgent care visits;

CTAP101 | CTAP101-CL-2014 | CTAP101-CL-2014 Protocol VV-TMF-183735 | Version 8.0 dated 16 Nov 2021

Protocol CTAP101-CL-2014	OPKO Pharmaceuticals, LLC
CTAP101 (calcifediol) Extended-release Capsules	Page 12 of 82

- 4. Incidence of oxygen saturation below 94% (without supplemental oxygen);
- 5. Incidence of hospitalizations (mean duration of hospitalization will also be presented);
- 6. Incidence of requirement for mechanical ventilation; and,
- 7. Mortality rate (as incidence).

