6.10 Efficacy Analyses

6.10.1 Primary Efficacy Endpoints

The two primary efficacy endpoints will be tested hierarchically to maintain an overall one-sided alpha level of 0.025. Therefore, the test of resolution of symptoms based on the aggregate FLU-PRO Plus[©] symptom score will be performed only if the attainment of serum 25D levels \geq 50 ng/mL at Day 14 is significant at <0.025.

The first primary efficacy endpoint, attainment of serum 25D levels at ≥50 ng/mL, will be assessed with a Chi-square statistic at Day 14. The serum 25D levels will also be compared between treatment groups at Days 7, 21 and 28 with a Chi-square statistic.

The second primary efficacy endpoint is the number of days to resolution of symptoms, defined as a reduction in the aggregate FLU-PRO Plus[©] score for the selected five COVID-19 symptoms recorded on Day 0 (prior to study drug initiation) to or below 5 for a minimum of three consecutive days. The time to resolution is defined as the number of days from Day 1 (study drug initiation) to the first day of achieving the aggregate ≤5 score for a minimum of three consecutive days, provided that no score greater than 5 is recorded between the two qualifying scores. Resolution will be determined by the first two successive qualifying scores which span a minimum of three consecutive days. For clarity, resolution will be considered as having been achieved if two successive aggregate scores of ≤5 are recorded on the first day of this occurrence and on a subsequent day that is at least two days (but not more than 5 days) later even if no score has been recorded between the two days. Missing symptom score values will be handled as described in Section 6.2. The number of days to resolution will be analyzed with a Cox proportional hazards model with covariates (baseline aggregate FLU-PRO Plus[©] score for the selected five COVID-19 symptoms, baseline serum 25D, and body weight).

As a sensitivity analysis of the resolution of symptoms, a tipping point approach will be used starting with the analysis in which scores are available for three consecutive days, with no missing interval, followed by increasing numbers of missing days in the up to five-day interval, that is, 1, 2 and 3 missing days between the two consecutive qualifying scores.

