Subgroup analyses for the primary efficacy endpoints will be based on age (\leq 40 or >40 years), severity of the selected five COVID-19 symptoms at baseline (aggregate FLU-PRO Plus[©] score of \leq or > the median score), attained serum 25D at Day 14 (below, within or above the targeted range of 50 to 100 ng/mL), body weight (\leq 100 or >100 kg), BMI (\leq 30 or >30), dosing compliance (<80% or \geq 80%), gender, race, ethnicity, number of comorbidities (<1 or \geq 1), duration of treatment (\leq 10 or >10 days) and prior or intercurrent COVID-19 vaccination and/or monoclonal antibody therapy for COVID-19.

In addition, the number of days to resolution of the five aggregated symptoms will be compared based on the serum 25D level at Day 14 (<50 ng/mL vs 50 to 100 ng/mL and 50 to 100 ng/mL vs >100 ng/mL), regardless of the assigned treatment group. The comparisons will be done using a Chi-square test. Frequency of relapses will be calculated, if possible, to account for potential worsening of symptoms after resolution (defined above), with relapse being defined as achieving an aggregate FLU-PRO Plus[©] score >5 for a minimum of three consecutive days.

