14.2.1.13 Resolution of COVID-19 Symptoms Based on FLU-PRO Plus COVID-19 Five Symptom Aggregate Score Based on Serum 25D Level at Day 7: Full Analysis Population 14.2.1.14 Resolution of COVID-19 Symptoms Based on FLU-PRO Plus COVID-19 Five Symptom Aggregate Score Based on Serum 25D Level at Day 7: Per Protocol Population 14.2.1.15 Resolution of COVID-19 Symptoms Based on FLU-PRO Plus COVID-19 Five Symptom Aggregate Score Based on Serum 25D Level at Day 14: Full Analysis Population 14.2.1.16 Resolution of COVID-19 Symptoms Based on FLU-PRO Plus COVID-19 Five Symptom Aggregate Score Based on Serum 25D Level at Day 14: Per Protocol Population Resolution of COVID-19 Symptoms Based on FLU-PRO Plus Aggregate Score 14.2.1.17 Symptoms Based on Serum 25D Level at Day 21: Full Analysis Population Resolution of COVID-19 Symptoms Based on FLU-PRO Plus Aggregate Score 14.2.1.18 Symptoms Based on Serum 25D Level at Day 21: Per Protocol Population Resolution of COVID-19 Symptoms Based on FLU-PRO Plus COVID-19 Five 14.2.1.19 Symptom Aggregate Score Based on Serum 25D Level at Day 28/ET: Per **Protocol Population** Resolution of COVID-19 Symptoms Based on FLU-PRO Plus COVID-19 Five 14.2.1.20 Symptom Aggregate Score Based on Serum 25D Level at Day 28/ET: Per **Protocol Population** 14.2.1.21 COVID-19 Symptom Relapse After Initial Resolution Based on FLU-PRO Plus COVID-19 Five Symptom Aggregate Score: Full Analysis Population COVID-19 Symptom Relapse After Initial Resolution Based on FLU-PRO Plus 14.2.1.22 COVID-19 Five Symptom Aggregate Score: Per Protocol Population Sensitivity Analysis for Resolution Based on Number of Consecutive Days with 14.2.1.23 FLU-PRO Plus COVID-19 Aggregate Score <=5: Full Analysis Population 14.2.1.24 Sensitivity Analysis for Resolution Based on Number of Consecutive Days with FLU-PRO Plus COVID-19 Aggregate Score <=5: Per Protocol Population Missing FLU-PRO Plus Questionnaire Responses: Full Analysis Population 14.2.1.25 14.2.1.26 Missing FLU-PRO Plus Questionnaire Responses: Per Protocol Population

SECONDARY EFFICACY ENDPOINTS

- 14.2.2.1 Time to Resolution of COVID-19 Symptoms Based on FLU-PRO Plus COVID-19 Five Symptom Aggregate Score Using Alternate Method for Identifying Resolution: Full Analysis Population
- 14.2.2.2 Time to Resolution of COVID-19 Symptoms Based on FLU-PRO Plus COVID-19 Five Symptom Aggregate Score Using Alternate Method for Identifying Resolution: Per Protocol Population

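### Days to symptom resolution are compared between Day-14 serum 25D groups, arms pooled, by a Chi-square test with no stated day, covariates or landmark; Day-14 25D is also a circular subgroup for primary endpoint 1 at Day 14

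*SAP*

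**What the plan says.** SAP 6.10.1 adds a comparison to the primary analyses: "In addition, the number of days to resolution of the five aggregated symptoms will be compared based on the serum 25D level at Day 14". It contrasts three Day-14 25D groups (<50 v 50 to 100, and 50 to 100 v >100 ng/mL) and is made "regardless of the assigned treatment group". The method is one sentence: "The comparisons will be done using a Chi-square test". The protocol has the same plan in 9.10.1 and in the Synopsis ("The comparison will be done using a Chi-square test").

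Earlier in SAP 6.10.1, for the same variable as primary endpoint 2: "The number of days to resolution will be analyzed with a Cox proportional hazards model with covariates". Those covariates are baseline aggregate score, baseline 25D and body weight.

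SAP 6.2 describes the time-to-event analysis in terms of the proportion resolved out of the total population, but gives no day. The related tables in SAP 8.1 (14.2.1.13 to 14.2.1.20) speak of resolution rather than time to resolution and also give no day, for example "Symptom Aggregate Score Based on Serum 25D Level at Day 14: Full Analysis".

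The subgroup list for both primary endpoints in SAP 6.10.1 includes "attained serum 25D at Day 14 (below, within or above the targeted range of 50 to 100 ng/mL". Endpoint 1 is itself 25D of at least 50 ng/mL at Day 14 (SAP 5.2). Tables 14.2.1.3 and 14.2.1.4 plan attainment by visit and subgroup and exclude no factor.

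**The concern.** There are four difficulties.

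- **Test.** A censored time is given a Chi-square test. If a proportion is meant, the day is missing. Day 28 appears in the sample-size text and Day 10 in secondary endpoint 2, but neither is tied to this comparison.
- **Timing.** The 25D level is measured at Day 14 ± 2 (Protocol 7.5), after many subjects will already have resolved. For them the exposure is recorded after the outcome.
- **Mixing.** Active subjects will fill the higher 25D groups, so a pooled contrast partly repeats the comparison of arms. Body weight, which Protocol 3.2 says affects the 25D rise, is not adjusted for.
- **Circularity.** Splitting endpoint 1 at Day 14 by Day-14 25D splits the outcome by itself.

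The trial hypothesis is that raising 25D to at least 50 ng/mL attenuates illness (Protocol 3.2). A small p-value here would be read as direct support for that mechanism, and nothing in the visible text marks it as exploratory or non-randomised.

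**Working it through.** The comparison has no sample size, power or alpha of its own to reproduce. The inputs are from SAP 3.3: 80 per arm, 50% v 70% resolved by Day 28, hazard ratio 1.74, and 25% v 75% attaining 50 ng/mL (stated for Day 28). Check of the hazard ratio: ln(0.3)/ln(0.5) = 1.737, which agrees with 1.74. Constant hazard over time is my assumption.

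**1. Outcomes before the grouping variable.** Resolved by day d = 80(1 − 0.5^(d/28)) + 80(1 − 0.3^(d/28)).

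| Day | Resolved | Share of Day-28 total |
|---|---|---|
| 7 | 12.7 + 20.8 = 33.5 | 35% |
| 12 | 52.8 | 55% |
| 14 | 23.4 + 36.2 = 59.6 | 62% |
| 16 | 66.0 | 69% |
| 28 | 96.0 | 100% |

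By Day 42 the total is 118.6, so the Day-14 share is 59.6/118.6 = 50%. The planned Day-7 tables ("Symptom Aggregate Score Based on Serum 25D Level at Day 7: Full Analysis") reduce this problem but do not remove it.

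**2. Dependence on the unstated day.** On the same model, control v active resolved is 22% v 35% at Day 10, 29% v 45% at Day 14, 50% v 70% at Day 28 and 65% v 84% at Day 42. The contrast depends on which day is chosen.

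**3. Arm mix.** As an illustration, collapse to <50 v ≥50 ng/mL and apply 25%/75% attainment at Day 14. Suppose level is unrelated to outcome within each arm.
- Below 50: (60 × 0.5 + 20 × 0.7)/80 = 55% resolved.
- 50 or above: (20 × 0.5 + 60 × 0.7)/80 = 65% resolved.
- Normal approximation, 80 v 80, counting rejections in the expected direction: null SE = √(0.6 × 0.4 × 2/80) = 0.0775; alternative SE = √((0.55 × 0.45 + 0.65 × 0.35)/80) = 0.0771; power = Φ((0.10 − 1.96 × 0.0775)/0.0771) = 25%.
- Simulation (200,000 trials, two-sided 0.05), pooled Chi-square v arm-stratified test: 24.0% v 5.0%. At 25%/50% attainment, 9.7% v 4.9%. At 10%/90%, 53.4% v 4.9%.
- With equal arms (60%/60%), the pooled test rejects in 4.7%, so there is no inflation.

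**4. Body weight.** Protocol 3.2 gives a rise of 20 to 35 ng/mL after loading, depending on weight, and 0.6 per maintenance dose. With ten maintenance doses (Days 4 to 13), the Day-14 level is baseline + (20 to 35) + 6. A baseline of 20 gives 46 to 61, so weight decides the group. A baseline of 25 gives 51 to 66, so it does not.

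**5. Circularity.** At Day 14, attainment is 0% in the below group and 100% in the within and above groups, in both arms. The arm difference is zero and the Chi-square is undefined.

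**6. What a landmark analysis would have.** Unresolved at Day 14: 56.6 + 43.8 = 100.4 subjects. Later events: 96.0 − 59.6 = 36.4 to Day 28, and 118.6 − 59.6 = 59.0 to Day 42. Detectable HR at 80% power = exp(2.80/√(E·q)), where q = 0.25 for even groups and 0.1875 for a 25%/75% split within arm.
- To Day 28: 2.53 and 2.92.
- To Day 42: 2.07 and 2.32.

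These ignore the correlation of 25D group with baseline 25D and weight. If those two explained 30% of the group indicator (assumed), the 2.92 would become exp(2.80/√(36.4 × 0.1875 × 0.70)) = 3.6.

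**The case against.** SAP 6.2 points towards proportion resolved, with unresolved subjects kept in the denominator. A Chi-square on a two-way table is then an ordinary test, and the defect in the test shrinks to a missing day, perhaps end of follow-up. A log-rank Chi-square cannot be excluded either, although elsewhere the SAP uses Chi-square for proportions and names Cox for times. This part stands, but it does not answer the timing or the pooling.

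By-arm views are already planned. Secondary endpoint 9 gives proportions by arm and 25D level, and the endpoint-2 25D subgroup gives time to resolution (Tables 14.2.1.11 and 14.2.1.12). A reader might infer that the subgroup is unadjusted. No text says so, and since it follows the Cox specification it may well use the same covariates. These outputs lower the risk of misreading but do not repair the pooled p-value.

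The 24-25% figure might be read as a general false-positive rate. It is not. It needs a real drug effect that is unrelated to 25D level within arm. The drug is 25-hydroxyvitamin D3 itself; if it acts only through 25D, the arm mix is not bias. What remains is that the pooled test cannot tell these two cases apart.

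The 0%/100% cells would be obvious to any reader, and the attainment results at Days 7, 21 and 28 in the same tables are not circular. Part of the protocol's exploratory text is also redacted, so the absence of an exploratory label is confirmed only for the visible text.

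**Conclusion.** The point holds as a should-fix. As written, the comparison has no defined day or adjustment, groups subjects by a level measured after half or more of the expected resolutions, and mixes that level with arm. The 62% and 50% figures rest on the plan's rates and constant hazard. The 24-25% also rests on using the Day-28 attainment rates at Day 14 and on no within-arm relation between level and outcome.

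A reader might infer that the trial's primary conclusion is at risk. The documents do not support that: both primary tests compare randomised arms in a fixed sequence at one-sided 0.025, and this comparison lies outside that sequence. The harm is confined to how a level-response result would be interpreted. The circularity is exact, but only for endpoint 1 at Day 14.

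**What to change.** In SAP 6.10.1, with matching protocol text:

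- Replace the Chi-square with a time-to-event comparison that starts from the 25D measurement: either a Day-14 landmark in subjects still unresolved, or a time-updated 25D category. Stratify by arm and adjust for baseline score, baseline 25D and body weight.
- If proportion resolved is intended, state the day and apply the same landmark and stratification.
- Label the comparison exploratory and non-randomised, and report an estimate with its interval rather than relying on a p-value.
- Drop attained Day-14 25D as a subgroup for endpoint 1 at Day 14. The Day 7, 21 and 28 attainment results may stay as descriptive.
- Report endpoint-2 results by attained 25D, and by the other post-dose subgroups (compliance, treatment duration, intercurrent therapy), as descriptive and non-randomised.

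The cost is SAP wording and a few re-programmed tables, on data already collected. The real price is precision: the landmark analysis could detect only a hazard ratio of at least about 2.5 to 2.9 to Day 28, and larger once collinearity with baseline 25D and weight is counted.

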6.10.2 Secondary Efficacy Endpoints

The following secondary endpoints will be tested statistically with methods described below, and the resulting nominal p-value will be reported for evaluation:

1. The number of days to resolution of five symptoms (trouble breathing, chest congestion, dry or hacking cough, body aches and pains, and chills and shivering), as measured by the FLU-PRO Plus[©] questionnaire, with resolution defined as the first aggregate symptom score of ≤5 which is maintained for a minimum of three consecutive days (see Section 5.2), with no individual symptom score >1;

- 2. Resolution, defined as the first score of ≤5 which is maintained for a minimum of three consecutive days (without subsequent relapse), for the aggregate five COVID-19 symptoms (trouble breathing, chest congestion, dry or hacking cough, body aches and pains, and chills and shivering) and for each individual symptom, defined as a score of 0 or 1, as measured by the FLU-PRO Plus[©] questionnaire as of Day 10;
- 3. Incidence of emergency room/urgent care visits;
- 4. Incidence of oxygen saturation below 94% (or requirement for supplemental oxygen);
- 5. Incidence of hospitalizations (mean duration of hospitalization will also be presented);
- 6. Incidence of requirement for mechanical ventilation; and,
- 7. Mortality rate (as incidence).

Endpoints listed will be summarized. For the analysis of the 34 individual symptoms assessed by the FLU-PRO Plus[©] questionnaire, a threshold of ≤1 is appropriate because it describes minor symptom severity (at worst "a little bit") which seems unlikely to presage a poor outcome. Analysis of the resolution of individual symptoms will be performed using a logistic regression, with baseline symptom score, baseline 25D level, and body weight as covariates. Analysis of the secondary endpoints based on incidence will be performed with a Chi-square test. Mean duration will be analyzed with ANCOVA. Mortality will be analyzed as incidence, with logistic regression with baseline symptom score, baseline 25D level and body weight as covariates. Rates only will be reported if there are too few deaths to be formally analyzed.

[figure not shown]
The severity, duration and clinical course of COVID-19 illness will be compared between treatment groups by analyzing changes in quality-of-life assessments recorded on the FLU-PRO Plus[©] questionnaire. Five of the six items from the questionnaire to be analyzed are: "Overall, how severe were your infection symptoms today?", "Overall, how were your infection symptoms today compared to yesterday?", "How much did your infection symptoms interfere with your usual activities today?", "Have you returned to your usual activities today?", "In general, how would you rate your physical health today?", and "Have you returned to your usual health today?" The scores for: symptom severity range from 0 (no infection symptoms today) to 4 (very severe); symptoms today range from 1 (much better) to 7 (much worse); symptom interference range from 1 (not at all) to 5 (very much). The first of two consecutive scores of ≤ 1 spanning at least three days and no more than five days will be considered the day of resolution, provided that no intervening scores of >1 are recorded. The scores for return to usual activities or health are either "yes" or "no", and the first occurrence of "yes" will be deemed to be day of resolution provided that a second "yes" is recorded no more than 5 days later without an intervening "no". The remaining sixth item to be analyzed is: "physical health range from 1 (poor) to 5 (excellent). The first of two consecutive scores of >4 spanning at least three days and no more than five days will be considered the day of resolution, provided that no intervening scores of <4 are recorded. Each item will be compared between treatment groups using a Cox proportional hazards model with covariates (aggregate FLU-PRO Plus[©] score for the selected five COVID-19 symptoms at baseline, serum total 25D at baseline, and body weight).

The clinical course of COVID-19 will be examined by subgroups defined by serum total 25D levels <50 ng/mL, 50 to 100 ng/mL and >100 ng/mL at Days 7, 14, 21 and 28.

 	

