9.10.2 Secondary Endpoints

The following secondary endpoints will also be tested statistically with methods described below, and the resulting nominal p-value will be reported for evaluation:

1) The number of days to resolution of five symptoms (trouble breathing, chest congestion, dry or hacking cough, body aches and pains, and chills and shivering), as measured by the FLU-PRO Plus[©] questionnaire, with resolution defined as the first aggregate symptom score of \leq 5 which is maintained for a minimum of three consecutive days, with no individual symptom score >1;

Protocol CTAP101-CL-2014	
CTAP101 (calcifediol) Extended-release Capsule	s

- 2) Resolution, defined as the first score of ≤5 which is maintained for a minimum of three consecutive days (without subsequent relapse), for the aggregate five COVID-19 symptoms (trouble breathing, chest congestion, dry or hacking cough, body aches and pains, and chills and shivering) and for each individual symptom, defined as a score of 0 or 1, as measured by the FLU-PRO Plus[©] questionnaire as of Day 10;
- 3) Incidence of emergency room/urgent care visits;
- 4) Incidence of oxygen saturation below 94% (or requirement for supplemental oxygen);
- 5) Incidence of hospitalizations (mean duration of hospitalization will also be presented);
- 6) Incidence of requirement for mechanical ventilation; and,
- 7) Mortality rate (as incidence).

Endpoints listed will be summarized. For the analysis of individual symptoms in endpoint #2 above, the threshold of ≤ 1 is appropriate because it describes minor symptom severity (at worst "a little bit") which seems unlikely to presage a poor outcome. Analysis of the resolution of individual symptoms will be performed using a logistic regression, with baseline symptom score, baseline 25D level, and body weight as covariates. Analysis of the secondary endpoints based on incidence will be performed with a Chi-square test. Mean duration will be analyzed with analysis of covariance (ANCOVA). Mortality will be analyzed as incidence, with logistic regression with baseline symptom score, baseline 25D level and body weight as covariates. Rates only will be reported if there are too few deaths to be formally analyzed.

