5.3 Secondary Efficacy Endpoints

The secondary endpoints are:

- 1. The number of days to resolution of five symptoms (trouble breathing, chest congestion, dry or hacking cough, body aches and pains, and chills and shivering), as measured by the FLU-PRO Plus[©] questionnaire, with resolution defined as the first aggregate symptom score of ≤5 which is maintained for a minimum of three consecutive days, with no individual symptom score >1:
- 2. Resolution, defined as the first score of ≤5 which is maintained for a minimum of three consecutive days (without subsequent relapse), for the aggregate five COVID-19 symptoms (trouble breathing, chest congestion, dry or hacking cough, body aches and pains, and chills and shivering) and for each individual symptom, defined as a score of 0 or 1, as measured by the FLU-PRO Plus[©] questionnaire as of Day 10;
- 3. Incidence of emergency room/urgent care visits;
- 4. Incidence of oxygen saturation below 94% (or requirement for supplemental oxygen);
- 5. Incidence and duration of hospitalizations;
- 6. Incidence of requirement for mechanical ventilation;
- 7. Mortality rate (as incidence);
- 8. Severity and duration of COVID-19 illness as evidenced by quality-of-life measures including ability to perform usual activities and opinion of overall health status, using the FLU-PRO Plus[©] questionnaire; and,
- 9. Clinical course of COVID-19 as a function of serum 25D concentrations of <50 ng/mL, 50 to 100 ng/mL and >100 ng/mL at Days 7, 14, 21 and 28, defined as the proportion of subjects in each treatment group with a total score of ≤ 5 for the selected five COVID-19 symptoms (trouble breathing, chest congestion, dry or hacking cough, body aches and pains, and chills and shivering) using the FLU-PRO Plus[©] questionnaire.

Endpoint items 3-7 are all based on incidence over the entire 42 day study period.

Once daily (during a 24 hour period starting in the evening before bedtime), subjects will record their ability to perform usual activities and their opinion of overall health status in an electronic diary using FLU-PRO[©] Plus questionnaire.

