- 14.2.2.3 Summary of Secondary Efficacy Endpoints Related to Resolution of FLU-PRO Plus Symptoms on or Before Day 10: Full Analysis Population
- 14.2.2.4 Summary of Secondary Efficacy Endpoints Related to Resolution of FLU-PRO Plus Symptoms on or Before Day 10: Per Protocol Population

14.2.2.5 Summary of Other Secondary Efficacy Endpoints: Full Analysis Population 14.2.2.6 Summary of Other Secondary Efficacy Endpoints: Per Protocol Population Supplemental Analysis of Time to Resolution of Individual FLU PRO Plus 14.2.2.7 Symptoms: Full Analysis Population Supplemental Analysis of Time to Resolution of Individual FLU PRO Plus 14.2.2.8 Symptoms: Per Protocol Population 14.2.2.9 Severity of COVID-19 Illness as Evidenced by Quality of Life Measures Using the FLU-PRO Plus Questionnaire at Each Visit: Full Analysis Population Severity of COVID-19 Illness as Evidenced by Quality of Life Measures Using 14 2 2 10 the FLU-PRO Plus Questionnaire at Each Visit: Per Protocol Population Duration of COVID-19 Illness as Evidenced by Quality of Life Measures Using 14.2.2.11 the FLU-PRO Plus Questionnaire: Full Analysis Population: Full Analysis Population 14.2.2.12 Duration of COVID-19 Illness as Evidenced by Quality of Life Measures Using the FLU-PRO Plus Questionnaire: Per Protocol Population 14.2.2.13 Clinical Course of COVID-19 as a Function of Serum 25D Concentration 50 ng/mL by Visit: Full Analysis Population Clinical Course of COVID-19 as a Function of Serum 25D Concentration 30 14.2.2.13.1 ng/mL by Visit: Full Analysis Se Clinical Course of COVID-19 as a Function of Serum 25D Concentration 100 14.2.2.13.2 ng/mL by Visit: Full Analysis Population 14.2.2.14 Clinical Course of COVID-19 as a Function of Serum 25D Concentration 50 ng/mL by Visit: Per Protocol Population 14.2.2.14.1 Clinical Course of COVID-19 as a Function of Serum 25D Concentration 30 ng/mL by Visit: Per Protocol Population Clinical Course of COVID-19 as a Function of Serum 25D Concentration 100 14.2.2.14.2 ng/mL by Visit: Per Protocol Population

SAFETY OUTPUTS

14.3.1.1	Overall Summary of Subjects with Treatment-Emergent Adverse Events: Safety Population
14.3.1.2	Incidence of Treatment-Emergent Adverse Events by SOC and Preferred Term: Safety Population
14.3.1.3	Incidence of Serious Treatment-Emergent Adverse Events by SOC and Preferred Term: Safety Population

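### The plan tests mean hospitalisation duration by ANCOVA without saying whether non-admitted subjects count as zero; if only admitted subjects are averaged, the comparison can point against a drug that prevents admissions

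*SAP*

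**What the plan says.** SAP 5.3 defines the fifth secondary endpoint as "Incidence and duration of hospitalizations". In SAP 6.10.2 the corresponding item in the list of tested endpoints reads "Incidence of hospitalizations (mean duration of hospitalization will also be presented". That list is introduced with the statement that "the resulting nominal p-value will be reported for evaluation". Two methods follow. For incidence: "Analysis of the secondary endpoints based on incidence will be performed with a Chi-square test". For duration: "Mean duration will be analyzed with ANCOVA". Protocol 9.10.2 has the same sentence ("Mean duration will be analyzed with analysis of covariance (ANCOVA"), so the two documents agree and no precedence question arises.

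On the observation window, SAP 5.3 says "Endpoint items 3-7 are all based on incidence over the entire 42 day study period", which describes incidence and not duration. The output for this group of endpoints is "Summary of Other Secondary Efficacy Endpoints: Full Analysis Population" (SAP 8.1, Table 14.2.2.5), with a per-protocol counterpart (Table 14.2.2.6).

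Neither document states:
- the denominator of the mean;
- a rule for death in hospital, repeat admissions or stays still running at Day 42;
- the ANCOVA covariates, although the Cox and logistic models in SAP 6.10 name theirs;
- what happens if few subjects are admitted, although SAP 6.10.2 has such a fallback for mortality.

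The missing-data and tipping-point rules in SAP 6.2 cover incidence, not length of stay.

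**The concern.** A mean duration of hospitalisation usually means length of stay among people who were hospitalised. A programmer averaging the recorded stays would produce exactly that. But admission happens after randomisation and is itself tested as an outcome in the same section, so the admitted subjects in the two arms are not a randomised comparison. If the drug keeps the milder cases out of hospital, those still admitted on active are the sicker ones and their average stay is longer. The report could then carry a nominal p-value against the drug for duration next to an incidence result in its favour, with both produced by the same benefit.

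Numbers are a second problem. The trial enrols mild to moderate disease and excludes subjects with oxygen saturation below 94% (Protocol 4.2 and 4.3), so admissions may be few. ANCOVA on a handful of skewed stays is fragile.

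**Working it through.** The documents give no admission rate, length of stay, effect or power for this endpoint, so there is no planned figure to reproduce. The check asks how far the admitted-only mean can mislead under stated assumptions.

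**Inputs.** From the documents: about 80 subjects per arm (Protocol 5.3.4, SAP 3.1). Assumed: placebo admission risk of 5%, 10% or 20%; half of admissions short (2 days) and half long (8 days); active prevents 50% or 80% of the short admissions and changes nothing else.

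**Formulas.** Let *s* and *l* be the risks of a short and a long admission in an arm.
- Mean stay among the admitted = (2*s* + 8*l*) / (*s* + *l*)
- Mean days per randomised subject = 2*s* + 8*l*, with zero for those not admitted

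**At 10% placebo risk.**
- Placebo, *s* = 0.05, *l* = 0.05: per subject 0.10 + 0.40 = 0.50 days; among admitted 0.50 / 0.10 = 5.0 days.
- Active, 50% of short stays prevented, *s* = 0.025: per subject 0.05 + 0.40 = 0.45; among admitted 0.45 / 0.075 = 6.0.
- Active, 80% prevented, *s* = 0.01: per subject 0.02 + 0.40 = 0.42; among admitted 0.42 / 0.06 = 7.0.

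The admitted-only mean moves against active (5.0 to 6.0 or 7.0 days) while days per randomised subject move in its favour (0.50 to 0.45 or 0.42).

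**Other risks.** The admitted-only means do not depend on the overall risk. The per-subject means scale with it.

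| Placebo risk | Expected admitted, placebo v active (50% / 80% prevented) | Days per subject, placebo v active (50% / 80% prevented) |
|---|---|---|
| 5% | 4 v 3 / 2.4 | 0.25 v 0.225 / 0.21 |
| 10% | 8 v 6 / 4.8 | 0.50 v 0.45 / 0.42 |
| 20% | 16 v 12 / 9.6 | 1.00 v 0.90 / 0.84 |

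**Simulation over the same grid.** An unadjusted two-sided t-test stands in for ANCOVA, because no covariates are given. A trial is comparable if each arm has at least two admitted subjects.
- Admitted only: active has the longer mean stay in about 61–96% of comparable trials, with nominal p<0.05 against active in about 3–39%. The low end of the second range depends on how trials with no variation in stay within either arm are handled.
- All subjects with zeros: active has the higher mean in about 33–42% of trials. That is sampling noise, since the expected difference favours active throughout.

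**Second set of assumptions.** Here stays are variable, with means of 4 and 12 days, and 50% or 100% of short admissions are prevented. The expected mean stay among the admitted is 8.0 days on placebo against 9.3 or 12.0 on active. Active looks longer in 61–93% of comparable trials, with nominal p<0.05 against it in 5–33%. With zeros included it looks worse in 27–43%. At 5% placebo risk, 27–45% of trials have fewer than two admitted subjects in an arm, so the comparison cannot sensibly be made.

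**The case against.** **The text.** A reader might infer that the plan compares only admitted subjects. It does not say so. The table shell names the Full Analysis Population, and where the SAP narrows a set for particular endpoints (SAP 4.3, individual symptoms and quality-of-life items) it says so; no narrowing is stated for duration. This stands as far as it goes: the defect is an unspecified denominator, not a stated restriction. But a population label on a table that covers several endpoints does not fix the denominator of a mean stay, and the admitted-only reading remains the ordinary one.

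**Deaths.** A reader might also infer that a death in hospital would be scored as a short, favourable stay. No such scoring is stated. There is simply no rule, and mortality is reported as its own endpoint.

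**The numbers.** The size rests on assumed inputs, and the reversal depends on which admissions are prevented. A drug that shortened stays, or prevented long ones, would not produce it. The direction figures are also not significance figures. At 10% risk with 80% of short stays prevented, active has the longer mean in about 88% of comparable trials, but nominal p<0.05 against it occurs in only about 17–19%. Nor do zeros make the picture clean: in that scenario active still looks worse in about 37% of trials, and a rank test over all subjects detects the benefit in only about 14%. All of this stands, which is why ranges are shown.

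**Consequence.** The result is one nominal secondary result beside a test of incidence that would show the admissions avoided. That limits the harm but does not remove the reason to define the analysis.

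**Conclusion.** The plan commits to an ANCOVA of mean hospitalisation duration without defining what is averaged. If the mean is over admitted subjects, the comparison is selected on an outcome and can point against a drug whose only effect is to prevent short admissions. Over the assumed grid (5–20% admitted, stays of 2 and 8 days, 50–80% of short stays prevented) it points that way in about 61–96% of comparable trials and reaches nominal significance against active in about 3–39%. Averaging over everyone, with zeros, restores an expected difference in the right direction; at this sample size it does not make the result precise.

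The documents do not support the stronger conclusions that the planned analysis definitely excludes non-admitted subjects, that deaths will be credited as short stays, or that the trial would probably report a significant harm. Severity is minor.

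**What to change.** Replace the duration sentence in SAP 6.10.2, before unblinding, with a definition along these lines:
- **Variable:** total days in hospital through Day 42, summed over repeat admissions, with stays still running at Day 42 cut off there.
- **Set:** all Full Analysis Set subjects, with zero for those not admitted.
- **Method:** bootstrap or permutation interval for the difference in means, or a rank test. If ANCOVA is kept, name its covariates.
- **Deaths:** state a rule, and repeat the analysis under an alternative rule. Giving deaths the worst value is one option, but it lets deaths dominate the measure and overlaps the mortality endpoint, so it is a choice to be made openly.
- **Stay among the admitted:** number admitted and mean stay shown descriptively, without a p-value.

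The cost is a short SAP edit, with no new data collection. The downsides are small: days per subject is less familiar than mean stay, and power will be low if few subjects are admitted.
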